#### 8 Data Derivation and Transformation

Data not originally part of CRF will be derived as follows:

- Subjects age [years] = [Date of Informed Consent Date of Birth] / 365.25
- Study Duration [days]= Date of Last Visit Date of First Visit + 1.
- BMI = Weight (kg) / Height (m) $^2$
- Coding of Adverse Events will be done using MedDRA version 21.0.
- Coding of Concomitant Medication will be done using WHODrug Dictionary 2018.
- Mayo score will be calculated as sum of 4 sub-scores: Stool Frequency Sub-score, Rectal Bleeding Sub-score, Endoscopic Finding Sub-score and Physician's Global Assessment Sub-score, each of which ranges from 0 (normal) to 3 (severe disease). The sub-scores are summed to give a total score that ranges from 0–12.
- Partial Mayo Score will be calculated as sum of the 3 following sub-scores:
   Stool Frequency Sub-score, Rectal Bleeding Sub-score and Physician's Global

Assessment Sub-score. The sub-scores are summed to give a total score that ranges from 0–9.

- UCEIS score will be calculated as sum of 3 sub-scores: Vascular pattern (which range from 0 to 2), Bleeding (range from 0 to 3) and Erosions and Ulcers (range from 0 to 3). The sub-scores are summed to give a total score that ranges from 0–8.
- Baseline values will be taken as the last available pre-treatment measures.

## 9 Statistical Analysis

All descriptive statistics will be provided by treatment group and overall, as relevant.

Numerical variables will be tabulated using mean, standard deviation, minimum, median, maximum and number of observations. Categorical variables will be tabulated using number of observations and percentages.

## 9.1 Subject Disposition

The following will be provided:

- Number and percent of subjects in each of the analysis populations (Safety, mITT, PP) by center and overall
- Listing of subjects excluded from each of the analysis populations along with reason for exclusion.
- Consort flow diagram (showing splits by previous anti-TNF treatment and treatment group)
- Number and percent of subjects who are eligible for randomization by site/ medical monitor.
- By-subject listing of the reason for not eligible for randomization
- Number and percent of subjects who meet all eligibility criteria at screening
- Number and percent of subjects who meet the inclusion/exclusion criteria at visit 2.

#### **Study termination**:

• Frequency of subjects who completed the trial

- For those subjects who did not complete the trial, frequency of the primary reason for premature discontinuation
- Listing of all dropouts along with reason for termination and supportive information if available, treatment and time of termination

#### **Protocol Deviations**

• Listing of protocol deviations including subject ID, date of deviation, visit/CRF term and protocol deviation.

#### 9.2 Baseline Characteristics

Baseline characteristics will be analyzed using the safety analysis population.

Descriptive statistics will be provided for the following:

- Demographic characteristics (Age, Gender, Race, Ethnicity, Height, Weight at screening and BMI).
- Number and percent of patients who have any relevant medical history
- By-subject listing of medical history including subject ID, center, Diagnosis/Symptoms, start date, stop date, whether ongoing.

#### **Previous Anti-TNF Treatment**

- Number and percent of subjects who received previous anti-TNF treatment
- By-subject listing of previous anti-TNF treatment including subject ID, center, trade name, dose, frequency, unit, route, start date, end date, anti-TNF treatment status, indication.

## 9.3 Safety

All safety analyses will be performed on the safety analysis population.

The following will be provided:

#### **Adverse Events (AEs):**

All treatment-emergent adverse events (including serious) will be tabulated using incidence tables with number and percentage of subjects by:

- System Organ Class (SOC) and Preferred Term
- Maximal Severity, System Organ Class (SOC) and Preferred Term

 Maximal Relation to study drug, System Organ Class (SOC) and Preferred Term

In the above frequency tables, the number and percentage of subjects who experienced AEs coded with the same preferred term will be tabulated by treatment group in descending order according to the incidence of AEs in the treatment group.

- By subject listing of all Adverse Events including subject ID, center, adverse
  event description, start date and time, intensity, whether treatment-emergent,
  relationship to study drug, action taken with study drug, corrective
  measurement, whether serious, seriousness specification, outcome, date and
  time of outcome
- Serious Adverse Events (SAEs):
   Same as the previous bullet (Adverse Events), limited to Serious Adverse Events only.

#### **Vital Signs (Body Measurements):**

- Descriptive statistics of weight, blood pressure (Systolic/ Diastolic), pulse rate, temperature and respiratory rate by visit, time point and treatment group.
- For each treatment visit (visits 2, 3 and 4) descriptive statistics of change from pre-dose of the given visit to each time point (15 minutes, 30 minutes, 2 hours and 4 hours post infusion), by treatment group.
- For each treatment visit (visits 2, 3, 4 at 4 hours post infusion time point) and follow up visits (visits 5, 6, 7 and 8) descriptive statistics of change from Screening will be provided by visit and by treatment group.
- Vital signs will also be presented graphically over time by treatment group.

#### **Laboratory Sample Collection**

• Descriptive statistics of laboratory results, including frequency of normality for tests over time and summary of shift in results post-treatment (e.g. shift tables or listings, as relevant)

#### **Tuberculosis Screen**

The following tables will be presented by visit and treatment group.

Frequency distribution of Patient's current TB status.
 For "Inactive"- frequency distribution of status (No evidence of active TB, Latent)

- Frequency distribution of Clinical examination (PPD)
- Frequency distribution of radiographic
- Frequency distribution of laboratory

For Tuberculosis screening- frequency distribution of test result (positive, negative)

For "Other"- frequency distribution of test result (positive, negative) by test.

#### **Physical Examination by body system:**

- Frequency distribution of evaluation (Normal /Non-Clinically Significant (NCS) Abnormal / Clinically Significant (CS) Abnormal) by body system, visit, and treatment group.
- Shift table of Normal / NCS Abnormal / CS Abnormal transitions from baseline to all subsequent visits. (Note, that "Other" category will not be presented in Shift tables).
- Listings of clinically significant abnormal physical examination results, including subject ID, Site, Visit, Body System and diagnosis.

#### **ECG**

- Descriptive statistics of ECG parameters (heart rate, RR, PR, QRS, QT, QTc) by visit, time point and treatment group.
- Frequency distribution of overall evaluation of ECG (Normal /Non-Clinically Significant (NCS) Abnormal / Clinically Significant (CS) Abnormal/not done) by visit, time point and treatment group.
- For each treatment visit (visits 2, 3 and 4)
  - Descriptive statistics of change from pre-dose to 30 minutes post-dose will be provided
  - Shift table of normal/abnormal NCS/abnormal CS transitions from predose to 30 minutes post-dose
- For each treatment visit (2, 3 and 4)
  - Descriptive statistics of change from screening to pre-dose will be provided.

- Shift table of normal/abnormal NCS/abnormal CS transitions from screening to pre-dose time point
- For each follow up visit (5, 6, 7)
  - Descriptive statistics of change from screening to visit will be provided.
  - Shift table of normal/abnormal NCS/abnormal CS transitions from screening to visit
- By-subject listings of abnormal ECG results, including subject ID, site, visit, time point, heart rate, RR, PR, QRS, QT, QTc intervals, abnormality description and whether clinically significant.

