8.3.7 Safety Analysis

The evaluation of safety endpoints will be carried out on the Safety set. Safety will be assessed by evaluation of adverse events and changes from baseline in vital signs, physical examination, infusion reactionand clinical laboratory safety test results. Individual subject listing will be provided. The observation period for all the safety endpoints spans from start of study medication up to study day 90.

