8.3.7.4 ECG

ECG parameters as assessed at baseline (i.e., pre-dosing, Day 0), at each scheduled time point during the observation period and at the last available timepoint during the observation period will be summarized by descriptive statistics (i.e., mean, median, standard deviation, standard error, quartiles, minimum and maximum) by treatment group both for observed values and for changes from baseline. In this evaluation, subjects will be included who had the baseline and the relevant assessment. Treatment-emergent ECG abnormalities (those that newly emerge during the observation period) will be summarized by treatment arm in terms of crude incidence rates.

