8.3.7.5 Vital Signs

Vital signs as assessed at baseline (i.e., pre-dosing, Day 0), at each scheduled time point during the observation period and at the last available time point during the observation period will be summarized by descriptive statistics (i.e., mean, median, standard deviation, standard error, quartiles, minimum and maximum) by treatment group both for observed values and for changes from baseline. Subjects who had the baseline and the relevant assessment will be included in this evaluation.

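### SAP cross-visit ECG and vital-sign changes run from Screening, not the protocol's pre-dose Day 0 baseline, and the ECG change and shift tables leave out Day 90

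*SAP*

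**What the plan says.** **Protocol.** Section 8.3.7.4 summarises "ECG parameters as assessed at baseline (i.e., pre-dosing, Day 0), at each scheduled time point during the observation period" and at the last one available, both as observed values and as changes from baseline. It also asks for the crude incidence, by arm, of ECG abnormalities that newly emerge. Section 8.3.7.5 has the same structure for vital signs: "Vital signs as assessed at baseline (i.e., pre-dosing, Day 0), at each scheduled time point during the observation period". Section 8.3.7 sets the time frame: "The observation period for all the safety endpoints spans from start of study medication up to study day 90". Section 5.6.4 schedules an ECG at every visit, and Visit 8 is marked in the schedules of both documents.

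**SAP.** Section 8 gives a general rule: "Baseline values will be taken as the last available pre-treatment measures". Section 9.3 does not apply it to these two domains:

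- Vital signs: for the 4-hour value at Visits 2, 3 and 4 and for Visits 5, 6, 7 and 8, "descriptive statistics of change from Screening will be provided by visit and by treatment group".
- ECG at treatment visits: change and shift from Screening to the pre-dose value at Visits 2, 3 and 4.
- ECG at follow-up: change and shift from Screening under the bullet "For each follow up visit (5, 6, 7", with Visit 8 not listed.
- Both domains: separate within-visit change from the same visit's own pre-dose value to its post-dose values.

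The SAP does not explain the use of Screening or the absence of Visit 8.

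**The concern.** The protocol states a reference value and a time frame for two safety domains. The SAP changes the reference in both and shortens the time frame in one, without saying so.

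The reference matters most for shift tables. A Screening reference can misplace a subject in either direction:

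- Normal at Screening, abnormal at Day 0 pre-dose, abnormal at Day 56: the SAP table shows a new abnormality, whereas the protocol baseline shows none.
- Abnormal at Screening, normal at Day 0 pre-dose, abnormal at Day 56: the SAP table shows no shift, whereas the protocol baseline shows a new abnormality.

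A subject whose ECG first becomes abnormal at Day 90 enters no shift table. The protocol's incidence of treatment-emergent ECG abnormalities would have caught such a subject, but SAP 9.3 does not plan it. Safety is part of the primary objective, so these are not peripheral outputs.

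**Working it through.** The point concerns no sample size, power or error rate. The check is to count the scheduled time points after the Day 0 pre-dose reading and see which reference the SAP gives each. The protocol reference is Day 0 pre-dose throughout. Early discontinuation and unscheduled visits are not counted.

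**ECG** (protocol 5.6.4 and Appendix A; SAP 9.3, ECG)

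| Time points | Number | SAP reference for change |
|---|---|---|
| Day 0, 30 min | 1 | Day 0 pre-dose |
| Days 14 and 28, pre-dose | 2 | Screening |
| Days 14 and 28, 30 min | 2 | Same visit's pre-dose only |
| Days 35, 42, 56 | 3 | Screening |
| Day 90 | 1 | None |

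Total: 1 + 2 + 2 + 3 + 1 = 9. Change from the protocol baseline is planned at 1 of 9.

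**Vital signs** (protocol 5.6.3 and Appendix A; SAP 9.3, Vital Signs)

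| Time points | Number | SAP reference for change |
|---|---|---|
| Day 0: 15 min, 30 min, 2 h, 4 h | 4 | Day 0 pre-dose (4 h also Screening) |
| Days 14 and 28, pre-dose | 2 | None |
| Days 14 and 28: 15 min, 30 min, 2 h | 6 | Same visit's pre-dose only |
| Days 14 and 28, 4 h | 2 | Same visit's pre-dose, and Screening |
| Days 35, 42, 56, 90 | 4 | Screening |

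Total: 4 + 2 + 6 + 2 + 4 = 18. Change from the protocol baseline is planned at 4 of 18.

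**Visit 8.** ECG change and shift are planned at 3 of 4 follow-up visits. The last planned table is at Day 56, which is 90 − 56 = 34 days before the observation period ends. In the same SAP section the vital-sign bullet names Visit 8, and the physical-examination shift table runs from baseline to all later visits. The ECG omission therefore looks like a drafting slip.

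**Can the protocol's table be rebuilt from the SAP's?** Only in part. For ECG, mean(Day 56 − Day 0) = mean(Day 56 − Screening) − mean(Day 0 − Screening), provided the same subjects contribute to both terms. The standard deviation, median and range do not follow from the two tables, and neither does any subject's shift category.

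**Weight of one subject.** With the full 42 subjects at 2:1, the arms have 42 × 2/3 = 28 and 42 × 1/3 = 14. One misplaced subject moves a shift cell by 1/28 = 3.6% in the active arm or 1/14 = 7.1% in the placebo arm.

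**The case against.** Several stronger readings are tempting, and the documents do not support them.

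- *All ECG and vital-sign changes are taken from Screening.* They are not. The within-visit tables use that visit's pre-dose value, which at Visit 2 is the protocol baseline itself.
- *Day 90 ECGs disappear from the report.* They do not. The parameter table and the normal/abnormal frequency table are by visit with no limit, and the abnormal-ECG listing has none either. A Day 90 finding judged clinically significant is an adverse event under protocol 7.1 and falls within the period for treatment-emergent events. What is missing is the paired transition.
- *Drift before Day 0 is hidden and biases the comparison.* For ECG, the SAP tabulates Screening to Visit 2 pre-dose separately. Screening readings precede randomisation and both arms receive the same premedication, so expected drift is equal in the two arms. Drift adds noise and can misplace individuals, but it does not favour an arm systematically.
- *Day 0 pre-dose is a drug-free value.* Under Version 8.0, oral dexamethasone is scheduled 18 to 24 hours before each infusion and so normally precedes the Day 0 reading. The SAP's safety set also counts prophylactic treatment as qualifying exposure. For these subjects the SAP section 8 rule could be read as pointing back to Screening, so the internal SAP conflict is less certain than the conflict with the protocol.

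The premedication argument is the best case for a Screening reference. However, the SAP does not make it, it cannot apply to subjects dosed before Version 8.0, and Version 8.0 of the protocol keeps pre-dose Day 0 as baseline while introducing the premedication. It supports showing Screening-based tables in addition, not in place of the protocol's.

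Visit 8 is also the visit with the lowest expected exposure. It falls 90 − 28 = 62 days after the last scheduled dose, or 62/20 = 3.1 to 62/16 = 3.9 half-lives of total drug on the protocol's 16 to 20 day estimate. That lowers the expected yield, but it does not remove the protocol's requirement.

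**Conclusion.** The point holds for the cross-visit tables. SAP 9.3 departs without explanation from the protocol's Day 0 reference for ECG and vital signs, and it omits Visit 8 from ECG change and shift. Change from the protocol baseline is planned at 1 of 9 ECG and 4 of 18 vital-sign time points. The ECG text also lacks the last-available summary and the treatment-emergent incidence that protocol 8.3.7.4 requires. Shift tables themselves are a SAP addition; the protocol asks for change and incidence.

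The effect is confined to descriptive safety reporting in an exploratory trial of up to 42 subjects. No efficacy result, error rate or sample size changes, and the documents do not support reading this as lost data or as bias between arms. The SAP should be corrected, but the issue does not threaten the trial's conclusions.

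This rests on two assumptions: that pre-dose Day 0 readings were taken as scheduled, and that SAP tables described as by visit include Visit 8.

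**What to change.** In SAP 9.3:

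1. Compute cross-visit ECG and vital-sign change, and ECG shift, from the pre-dose Day 0 value. Use Screening only where Day 0 is missing, and flag those subjects.
2. Add Visit 8 and the last available time point to the ECG change and shift tables.
3. Add a table of the crude incidence of treatment-emergent ECG abnormalities by arm.
4. Leave the within-visit tables as they are.
5. If Screening-based tables are wanted because premedication precedes the Day 0 reading, keep them as a labelled supplement and state that reason.
6. In SAP section 8, say whether pre-treatment means before study drug or before premedication.

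The cost is SAP wording and some extra programming. All the readings are already scheduled, so no new data are needed.

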#### **General Infusion Reaction (CRF Injection Site Reaction Assessment)**

• Frequency distribution of Skin Tolerability by visit, time point and treatment group.

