1.3.2 Allergic and Infusion Reactions

Monoclonal antibodies, including fully human antibodies, can cause allergic or non-allergic infusion reactions when administered intravenously, and three subjects in bertilimumab clinical trials have experienced infusion reactions, one serious. Accordingly, several precautions have been instituted in the protocol to decrease the risk of infusion reactions and possible anaphylaxis, including the administration of study drug^f in a controlled setting with ready availability of antihistamines, fluids, epinephrine, and staff trained in the management of anaphylaxis and a pre-study drug regimen with antihistamines, acetaminophen and corticosteroids.

Grading of infusion reactions will be made according to the criteria set forth in Appendix D, as are criteria for anaphylaxis, by definition, a grade 4 reaction. Management of-study drug infusion in the event of an infusion reaction is set forth in Appendix D as well; if additional interventions beyond interruption of-study drug infusion are indicated, then the investigator should manage the reaction according to his or her clinical judgement and any applicable institutional protocols.

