4.5 REMOVAL, REPLACEMENT, OR EARLY DISCONTINUATION OF SUBJECTS FROM THERAPY OR ASSESSMENT

Subjects are free to discontinue their participation in the study at any time and without prejudice to further treatment. The Investigator must withdraw any subject from the study if that subject requests to be withdrawn, or if it is determined that continuing in the study would result in a significant safety risk to the subject. Withdrawn subjects will not be replaced.

The subject's participation in this study may be discontinued due to the following reasons:

- Subject withdraws consent.
- Intolerable adverse event (any subject experiencing a grade 3 or 4 infusion reaction will be withdrawn from the study).
- Subject's need for medication prohibited by the protocol.

- The Investigator decides that continuing in the study would not be in the subject's best interest.
- The subject is noncompliant with the protocol.
- The subject becomes pregnant.
- Upon the decision of relevant Regulatory Authorities and/or the Institutional Review Board/Independent Ethics Committee (IRB/IEC).

Subjects who progress and/or relapse will be withdrawn from the study at the Investigator's discretion and will be able to receive local standard-of-care.

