<sup>6 The pretreatment dosing regimen is as follows: Dexamethasone 10 mg PO 24-18 hours prior to administration of bertilimumab. Acetaminophen 1000 mg PO 1 hour prior to administration of bertilimumab Loratadine 10 mg PO or cetirizine 10 mg PO one hour prior to the administration of bertilimumab. In the event that dexamethasone was not administered previously, then 10 mg dexamethasone IV may be administered one to three hours prior to bertilimumab administration.

At least 3 tissue samples are required from area of active inflammation at Screening. On Day 56 (or early discontinuation visit), at least 3 tissue samples are required from the same region where Screening biopsies were obtained. Additional biopsy samples may be collected at the Investigator's discretion for histological assessment.

<sup>8 Infusion reactions will be monitored for up to 4 hours following study drug administration and graded, as applicable, as appears in Appendix D

<sup>9 Biochemistry will include serum β-hCG at screening.

<sup>10 Blood samples for bertilimumab (PK analysis) will be collected pre-dose, 30 (+15) minutes (immediately post-dose) and 4 hours (± 20 minutes) following initiation of study drug infusion.

<sup>11Partial Mayo Score at Screening will be calculated from the Total Mayo Score.

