# 7 Definition of Endpoints

## 7.1 Safety Endpoints

Following are the study's safety endpoints:

- Treatment-emergent adverse events (TEAEs), including serious adverse events (SAEs)
- Infusion reactions
- Physical examination
- Vital signs (blood pressure, heart rate, temperature and respiratory rate)
- ECG
- Concomitant medications

• Laboratory evaluation (hematology, biochemistry, anti-bertilimumab antibodies).

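### The SAP's only dedicated infusion-reaction output is an undefined Skin Tolerability item; no SAP table is specified to count subjects with a reaction, or their worst Appendix D grade, by arm

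*SAP*

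**What the plan says.** SAP 7.1 lists "Infusion reactions" on its own line, apart from treatment-emergent adverse events. Protocol 2.2.4 also lists them separately, and protocol 8.3.7 names them among the safety assessments.

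Both documents require grading. Protocol 1.3.2: "Grading of infusion reactions will be made according to the criteria set forth in Appendix D". SAP Table 1, note 8: "Infusion reactions will be monitored for up to 4 hours following study drug administration and graded, as applicable, as appears in Appendix D". The SAP's table of contents shows no appendix, so note 8 can only mean the protocol's Appendix D, which has four grades.

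In SAP 9.3, the heading General Infusion Reaction is tied to the CRF's Injection Site Reaction Assessment. It carries one output: "Frequency distribution of Skin Tolerability by visit, time point and treatment group".

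The grade has a consequence in the trial. Protocol 4.5 states that "any subject experiencing a grade 3 or 4 infusion reaction will be withdrawn from the study".

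**The concern.** The output does not visibly match the endpoint. Protocol 5.6.6 describes infusion reactions as largely systemic, with chills, fever, nausea, bronchospasm and hypotension as well as rash. As far as the Appendix D table can be read, each of its four grades names at least one sign outside the skin. A skin item from an injection-site form would not obviously capture these.

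Safety is part of the primary objective, and this risk is known. Protocol 1.3.2 reports that "three subjects in bertilimumab clinical trials have experienced infusion reactions, one serious" and gives premedication as one of the precautions taken in response. A reader of the final report will want to know how many subjects in each arm had a reaction and how bad the worst one was. If the SAP is followed as written, no table is designed to answer that, and any grouping of records would be chosen after the data are seen.

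**Working it through.** The plan states no figure to reproduce. The check sets each planned output against two questions: does it count subjects with any infusion reaction by arm, and does it name the Appendix D grade?

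1. **Skin Tolerability (SAP 9.3).** It is split by visit and time point. A subject who reacts at more than one infusion appears in more than one row, so the rows do not add up to a number of subjects. The item is undefined and the SAP does not link it to Appendix D.
2. **TEAE tables (SAP 9.3).** Protocol 5.2 has post-infusion reactions recorded with the adverse events, so they enter these tables. The tables count subjects by arm, by preferred term and, for example, by "Maximal Severity, System Organ Class (SOC) and Preferred Term". Protocol 7.1 rates severity as mild, moderate or severe. No mapping from those three levels to the four Appendix D grades is given. Whether one reaction is entered as one event or as several signs is not stated, and the SAP sets no grouping term, flag or search.
3. **Adverse event listing (SAP 9.3).** The named fields run through items such as "event description, start date and time, intensity, whether treatment-emergent". An infusion-reaction flag and the grade are not among them, though the list need not be exhaustive.
4. **Discontinuations.** Protocol 8.3.7.1 summarises adverse events leading to discontinuation in the same way as TEAEs, so a grade 3 or 4 reaction could appear there by name. SAP 9.1 tabulates the primary reason for leaving. Grades 1 and 2 need not appear in either.
5. **All CRF data (SAP 10).** A collected grade would be listed, but a listing is not a summary by arm.
6. **General rules.** Protocol 8.3 asks for incidences in the different categories of ordered endpoints, by treatment group. Appendix D grades are ordered, so the rule can be read as covering them. SAP 9 gives only a generic format for categorical variables and does not turn the protocol's rule into a table for this endpoint.

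**Result.** SAP summaries that name the Appendix D grade: 0. SAP summaries specified to count subjects with any infusion reaction by arm: 0.

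**Illustration (assumed counts).** With the maximum of 42 subjects randomized 2:1, the active arm has 42 × 2/3 = 28. Suppose it yields three reaction entries, at three infusions or under three preferred terms.

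- All from one subject: 1/28 = 3.6%.
- From three subjects: 3/28 = 10.7%.

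Separate rows for visits or preferred terms need not show which. The system organ class row does not settle it either if the signs fall in different classes.

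**The case against.** The strongest reply is that infusion reactions are already covered. Sites are told to record them with the adverse events, and grading and the withdrawal rule both require the investigator to recognise a reaction as such. If it is entered under that name, the TEAE tables give subject counts by arm, severity and relationship. With at most 42 subjects and listings of all CRF data, reactions recorded as such can be found and counted by hand. Protocol 8.3 also has a general rule that fits an ordered grade. Finally, Skin Tolerability may be an old field label that now holds the grade.

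Much of this stands. A reader might infer that infusion reactions go unreported, that the protocol makes no provision for them, or that grade 3 and 4 withdrawals cannot appear as infusion reactions. The documents support none of these. Splitting a reaction into separate signs is possible, but no text says that it will happen.

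What the reply does not supply is a SAP table. Protocol 8 leaves full details of analyses and displays to the SAP, and for this endpoint the SAP provides only the Skin Tolerability line. Even if that field holds the grade, the output is by visit and time point and does not give each subject's worst grade.

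**Conclusion.** The SAP does not carry the protocol's general rule through to the infusion-reaction endpoint. Its dedicated output is an undefined item, and a grouped count by arm depends on how sites reported events. This is a reporting gap in an exploratory, descriptive trial. It does not threaten the trial's validity, and its weight is minor to moderate.

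Confidence is medium because the CRF is not in the documents. It would be too strong to say that Skin Tolerability excludes the grade: it may or may not hold it. If it does, what remains is a labelling point and a missing per-subject maximum. The number of affected reactions cannot be estimated from the documents, and the 3.6% and 10.7% only illustrate the ambiguity.

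**What to change.** In SAP 9.3, replace or supplement the Skin Tolerability line with wording such as: *Number and percent of subjects with at least one infusion reaction, and by maximum protocol Appendix D grade where collected (otherwise ungraded), by treatment group, overall and by infusion (Days 0, 14 and 28).*

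Also:

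- State before unblinding which records count. One option is any reaction on the infusion reaction assessment, or any adverse event that the investigator reported as an infusion or post-infusion reaction, with doubtful cases settled by blinded review.
- Flag subjects dosed before protocol version 8. The version history shows that Appendix D came with that version, and SAP 6.1 indicates that some subjects were treated before it. Their number is not given.
- If Skin Tolerability is the Appendix D grade, say so and add the per-subject maximum. Otherwise keep it as a separately labelled injection-site output.

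The cost is SAP wording, one small descriptive table and, if the CRF has no flag, a short blinded review of adverse event records. Some early events will be shown as ungraded. No new data collection or retrospective regrading is needed.
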